Assignment to Study Group: Participating children and their primary caregivers will be assigned to one of three groups. Participants will be stratified by age (18-35 months; >36 months) and developmental quotient (DQ<55; DQ ≥55) at project enrollment, prior to being randomized. After stratification, participants will be randomly assigned to the one of the three groups using random permuted blocks of 6. This approach has been shown to yield groups that are closely balanced with regard to size and relevant pre-treatment characteristics. All pre-treatment assessments will be collected prior to randomization to prevent bias during testing based on knowledge of future group placement.

b. Sources of Materials

The sources of data for this study will include: (1) direct assessment of child functioning using standardized assessments; (2) completion of standardized questionnaires by parents; (3) written survey completion by parents; and (4) videotaped coding of treatment processes. All data will be used exclusively for research purposes. All surveys and interviews will use codes rather than subject names. Only the PI and primary research team members will have access to subject identities. Procedures to minimize risk of loss of confidentiality are presented below.

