Child Measures: Child diagnostic testing will be conducted at pre-treatment. We will also examine specific child characteristics (cognitive ability level, language level, autism severity) that are predicted to be related to the impact of the parent-implemented interventions. We will administer the Autism Diagnostic Observation Scale, 2nd Edition (ADOS-2) to the child at pre-treatment. The ADOS-2 is a standardized protocol for observation of social and communicative behavior associated with a diagnosis of ASD that has been shown to have high reliability and discriminant validity. Recent longitudinal studies have demonstrated that diagnostic stability for children under age 3 is best when using DSM-IV based clinical judgment in conjunction with results from standardized diagnostic instruments, such as the ADOS. As in previous studies, this is the approach that will be used in the present study in order to determine a specific DSM-V diagnosis for each child. The PI has established research reliability on the ADOS. She will train the clinical research staff on these methods (as needed) and supervise all assessments. Child cognitive ability will be assessed using the Mullen Scales of Early Learning at T1. Child intentional communication with the parent will be scored from a parent-child interaction in the home at pre-treatment and post-treatment using weighted frequency of intentional communication. Language outcomes will be assessed at pre-treatment and follow-up using the

Mullen Scales of Early Learning, a parent report measure (the MacArthur-Bates Communicative Development Inventory) and the Vineland Adaptive Behavior Scales.

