Parent Measures: Parents will complete the Parenting Sense of Competence Scale at pre-treatment, post-treatment, and follow-up to assess parent self-efficacy. Using the videotapes of the parent-child interaction in the home at pre-, post-treatment, and follow-up, the research team will assess parent use of the intervention strategies. Parents will also be asked to provide demographic information and complete the Parent Expectancies for Therapy Scale, a measure of treatment expectancy, the Computer-Email-Web Fluency Scale, a measure of computer/internet fluency, at pre-treatment, and the Parenting Stress Index, a measure of parenting stress at pre-treatment. Parents will be asked to complete the Treatment Evaluation Inventory, measure of treatment acceptability, at the conclusion of treatment. Parents will complete the Additional Services Form to monitor the type and number of hours per week of all non-study treatments once per month throughout study participation.

c. Potential Risks

There are no known serious health or psychological risks related to participation in this study. Procedures to minimize risk of loss of confidentiality are presented in the following section. In addition, there are legal limits to the confidentiality of information obtained during the research study. All information obtained from participants will be held confidential unless there is serious threat of harm to a child or to self or others. These limitations will be addressed in the consent forms. Collection of data from participants will include standardized child assessment measures, standard parent questionnaires regarding their child's development and behavior, standard parent questionnaires about their well-being and satisfaction with treatment, and videotape recordings. Precautions will be applied to all collected data from these activities, which will be stored in a private, secure and confidential location at MSU. All participants will be made aware of how collected data will be handled.

Adequacy of Protection Against Risks

a. Recruitment and Informed Consent

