Primary caregivers of children with ASD will be recruited to participate in this study. Recruitment will be conducted through our ongoing contacts in Intermediate School District preschool special education programs and with clinicians at a number of sites in Lower Michigan. If a child appears to be eligible for the study, the clinician at that site will introduce the study to the family and present them with a brochure about the research project. In addition, a description of the study will be placed on the P.I.'s website which the public can access. Families who wish to participate will contact the project manager directly. The project manager will contact families to further explain the study, answer questions and schedule the first assessment session. The project manager will schedule an initial interview with the parents. At the beginning of that interview, the consent documents will be reviewed and written consent will be obtained from the parent. No child assent will be obtained because all children are expected to have significant cognitive and language delays that would prevent them from giving informed assent. Potential participants will be informed about the purpose and nature of the study and their rights as a participant. Written consent will be secured prior to the initiation of study participation. Participants will be assured of the maintenance of confidentiality and informed of their right to refuse to provide any data. Participants will be assured that data will only be reported in aggregate form without any individual identifying information. Parents will be compensated with \$25 for the pre-treatment, post-treatment, and follow-up assessment, totaling \$75. Each assessment period will consist of three to four hours of testing, involving direct child assessment, parent interview, and on-line data collection which may be completed across one to two visits. Applications for informed consent will be submitted to MSU's Human Research Protections Program. The nature of the proposed Research Plan is very similar to approved

studies currently being conducted by the P.I. As required, all amendments will be submitted for approval before being implemented. Annual project renewals will be submitted as required.

b. Protection Against Risks

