Parents will be provided with a report of their child's assessment results at pre-treatment and follow-up assessment. These reports will include the results of a comprehensive diagnostic evaluation. This report will only be shared with the parents, with our standard caveat that the purpose of the evaluation was as part of their participation in a research study and therefore should not necessarily be considered the equivalent of a clinical report. In our experience, parents usually find these reports to be quite helpful and many choose to share a copy with their child's service providers. Parents randomly assigned to the self-directed and therapist-assisted telehealth intervention groups will receive an internet-based parent training intervention that will be adapted from an evidence-based curriculum. Parents in the control group will be offered access to the self-directed telehealth intervention at completion of the study. There are no other direct anticipated benefits of participation in this study. There is, however, anticipated benefit of the knowledge gained from this study regarding parent-implemented interventions to improve outcomes for children with ASD and their families.

Importance of the Knowledge to be Gained

Knowledge gained from this research study will provide much needed information about ability to provide parent training for families with a child with ASD over the internet. Data available to date indicates great promise for parent training in terms of improving child outcomes and improving the quality of life for parents. Parent-delivered interventions can be implemented for relatively modest costs and provide services to a large number of families, in contrast to the high costs and limited availability of intensive child-directed services. While these parent-focused programs are not meant to replace intensive child-directed services for children with ASD, they appear to provide complimentary benefits and help to ameliorate the need for autism-specific services in areas where providers are in short supply. The provision of parent training over the internet has the potential to greatly increase the number of parents who can access these services, particularly in underserved areas where access to intervention providers is limited.

Statistical Analysis Plan

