Overall Approach. The current study will use the Intention-to-Treat model (ITT) in the analysis of the primary aims. The ITT approach requires that all participants who are randomly assigned be compared on outcomes regardless of their adherence to treatment, reasons for withdrawal, or missing responses. Accordingly, we will include all participants in data analysis, follow up participants who withdraw from treatment, and impute missing data, as described below.

Missing Data. We will use the Expectation Maximization (EM) algorithm in SPSS to impute missing data for analyses that require complete data (e.g., Process Macro).

Preliminary analyses. To determine the comparability of groups on non-treatment variables after randomization, group differences will be examined for all T1 pre-treatment and descriptive variables. If significant group differences are detected for a given variable, and the variable of interest, then the variable will be used as a covariate in subsequent analyses as appropriate.

We will also examine age and DQ effects and identify whether treatment effects are moderated by either.

Aim 1: To examine the comparative efficacy of self-directed and therapist-assisted *ImPACT Online* on parent outcomes at post-treatment and the 3-month follow-up. To test our primary hypotheses for Aim 1, we will use multilevel modeling with restricted maximum likelihood estimation to examine the effect of group assignment on our primary and secondary parent outcomes. Time point (pre-treatment, post-treatment, follow-up) will be coded as a categorical variable. Change over time across groups will be estimated with the main effect of time, and between-group differences in change in outcomes will be estimated with the group by time interaction.

Aim 2: To examine the comparative efficacy of self-directed and therapist-assisted *ImPACT Online* on child outcomes at the 3-month follow-up. Three measures of verbal language will be collected at pre-treatment and follow-up. If child language measures are sufficiently correlated with each other ($r > .50$), we will create an equally weighted composite variable by z-scoring and summing the language measures. ANCOVA will be used to test for mean differences between the three conditions at follow-up. Pretest values will be included as covariates.

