Aim 3: To examine whether pre-treatment parenting stress moderates the effects of *ImPACT Online* on parent fidelity and parent self-efficacy at post-treatment. Pre-treatment parenting stress will be included in the MLM models as a covariate. The pre-treatment parenting stress by time interaction will be used to determine whether pre-treatment parenting stress moderates change over time, irrespective of treatment group. The three-way interaction of pre-treatment parenting stress, group, and time will be used to examine whether the relationship between group assignment and change over time (i.e., group slopes) varied by pre-treatment parenting stress. A significant interaction will be followed up by simple slopes analyses.

Aim 4: To examine whether gains in parent fidelity (or parent self-efficacy) and child intentional communication at post-treatment mediate the effects of the *ImPACT Online* on child verbal language at the 3-month follow-up. We will conduct two serial mediation analyses using the PROCESS macro in SPSS to examine whether gains in parent fidelity (Mediator 1) and child intentional communication (Mediator 2) at post-treatment mediate the effect of *ImPACT Online* in child outcomes at follow-up. A second serial mediation analysis will be conducted to examine whether gains in parent self-efficacy (Mediator 1) and child intentional communication (Mediator 2) at post-treatment mediate the effect of *ImPACT Online* in child outcomes at follow-up.

Aim 5 (exploratory): To identify predictors of parent adherence to *ImPACT Online* for the two treatment groups. This exploratory aim will be addressed using a multiple regression approach in which level of therapist support (self-directed versus therapist assisted) and three individual-level factors (computer and internet fluency, expectancies of treatment, and treatment acceptability) serve as primary predictors of parent adherence. We will also examine sociodemographic variables as predictors as well.

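### The Aim 2 language composite rests one third, and probably two thirds, on report by parents who know whether they were treated, and no analysis of the directly tested measure alone is planned.

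*Combined protocol and SAP*

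**What the plan says.** The Child Measures paragraph (Sources of Materials) assesses language at pre-treatment and follow-up with the "Mullen Scales of Early Learning, a parent report measure (the MacArthur-Bates Communicative Development Inventory) and the Vineland Adaptive Behavior Scales". Only the MacArthur-Bates carries the parent-report label.

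Under Aim 2 of the Statistical Analysis Plan, if the measures correlate above .50, "we will create an equally weighted composite variable by z-scoring and summing the language measures". An ANCOVA then compares the three conditions at follow-up, with pretest values as covariates. Once the composite is formed, no analysis by measure or by informant is described.

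On knowledge of arm, the Potential Benefits section says: "Parents in the control group will be offered access to the self-directed telehealth intervention at completion of the study". The only stated protection is under Assignment to Study Group, and it covers pre-treatment assessments, which are completed before randomization. Nothing is said about who knows the arm at follow-up.

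The second Aim 4 analysis is to "examine whether gains in parent self-efficacy (Mediator 1) and child intentional communication (Mediator 2) at post-treatment mediate the effect of" the program on child outcomes at follow-up.

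**The concern.** Active-arm parents take the training and control parents wait for it, so no parent can be masked to treatment versus control. Any language score that a parent supplies at follow-up can therefore reflect a change in the child, a change in how the parent reports, or both. Equal weighting gives each parent-reported measure a full third of the composite.

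Neither of the plan's rules separates the two sources. The r > .50 condition cannot tell correlation due to language from correlation due to a shared informant. The pretest covariate cannot remove a reporting shift that begins after randomization.

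At stake is the interpretation of a positive active-versus-control result on child language. With only the composite prespecified, the trial could report improved language when what changed was parents' answers. The choice of whether and how to look at the Mullen alone would then be made after the results are known.

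**Working it through.** **Who supplies each measure**

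- Mullen: taken as direct testing. It is listed with the child assessments, and direct child assessment is the first data source.
- MacArthur-Bates: parent, as labelled.
- Vineland: not stated. The Sources of Materials list has direct assessment, parent questionnaires, parent surveys and video coding, with no teacher or other outside informant. Potential Risks mentions "standard parent questionnaires regarding their child's development and behavior", in the plural. The recruitment section describes each assessment as "involving direct child assessment, parent interview, and on-line data collection". The parent is the likely informant, but this is an inference, so both cases are computed.

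**Inputs**

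- N = 90 in three groups (protocol), taken as 30 per arm.
- Pretest to follow-up r = .65 for each measure (Power Analysis). It also applies to the composite if each correlation across measures and time is .65ρ: (3 × .65 + 6 × .65ρ)/(3 + 6ρ) = .65.
- Inter-measure correlation ρ from .5 (the plan's threshold) to .7 (assumed).
- Alpha .05, assumed because the SAP states none.
- Reporting shift b, in SD units, equal in both active arms and zero on the Mullen. This is assumed; the documents give no value.

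**The plan's own power figures**

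With the plan's covariate adjustment, the effective N is (90 − 3)/(1 − r²), used in a three-group noncentral F:

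- Fidelity (r = .35, f = .32): 80.9%, stated 80%.
- Self-efficacy (r = .75, f = .25): 89.0%, stated 90%.
- Child language (r = .65, f = .25): 87/.5775 = 150.6, giving 78.1% (79.0% by direct ANCOVA), stated about 90%.

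The method reproduces the first two. The shortfall for language is a separate matter and does not bear on this point.

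**Effect of a reporting shift with no true language effect**

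1. SD of the sum of three z-scores: √(3 + 6ρ), which is 2.449 at ρ = .5 and 2.683 at ρ = .7.
2. Composite shift in SD units: d = 2b/√(3 + 6ρ) if two measures shift, which is 0.75b to 0.82b. It is d = b/√(3 + 6ρ) if one shifts, which is 0.37b to 0.41b.
3. Group means are (0, d, d), so f = d√2/3 = 0.471d.
4. Noncentrality: λ = 90f²/(1 − .65²) = 90f²/.5775, with 2 and 86 df.

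Example, two measures, b = 0.3, ρ = .5: d = 0.6/2.449 = 0.245; f = 0.115; λ = 90 × 0.0133/.5775 = 2.08; rejection 22.6%.

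| b (SD) | MacArthur-Bates and Vineland shift | MacArthur-Bates only |
|---|---|---|
| 0.2 | 11-12% | 6-7% |
| 0.3 | 19-23% | 8-9% |
| 0.4 | 32-38% | 11-12% |

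Simulation (4,000 runs per setting) agrees: at b = 0.3 with two measures shifted it gave 22.6% (ρ = .5) and 18.6% (ρ = .7). The Mullen alone rejected in 4.5-5.8% of runs, as it must when its bias is set to zero.

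For reporting alone to produce the planned f = .25 on the composite, d must be .25/.471 = 0.53. With two measures shifted, that needs b = 0.53/0.816 = 0.65 (ρ = .5) to 0.53/0.745 = 0.71 (ρ = .7).

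**Contrast between the active arms**

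With equal b, the self-directed and therapist-assisted means both move by d, so their difference moves by d − d = 0.

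**Aim 4, self-efficacy model**

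The parent completes the self-efficacy scale and supplies one to two thirds of the composite. Shared-rater variance can therefore inflate the direct path from self-efficacy to language, and with it the simple indirect effect through self-efficacy. The second mediator, intentional communication, is scored from a parent-child interaction, not from parent report. A rater component shared by the other two variables does not inflate the serial path that runs through it.

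**The case against.** **The documents do not say that two of three measures are parent-reported.** This stands. A reader who knows the Vineland may take it as given, but the text labels only the MacArthur-Bates. With one affected measure the problem is real but much smaller, as the right-hand column of the table shows.

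**The shift b is invented.** It is assumed. The figures show what the design permits, not that parents will over-report.

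**Aim 2 is about comparing the two versions of the program.** A reader might infer that this comparison is biased too. Under an equal shift it is not. The bias affects active-versus-control contrasts and the three-group test. It would reach the comparison between versions only if the shift differed between the active arms, and the documents give no basis for assuming that.

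**The Aim 4 chain could be one rater answering twice.** This goes too far. The serial path runs through an observed mediator and is not inflated by shared-rater variance; only the direct and simple indirect paths through self-efficacy are exposed.

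**The Mullen may be biased as well.** This stands. No masking of follow-up examiners is described. The Mullen avoids parent-report bias but not necessarily examiner bias, so it is a useful check and not a final arbiter.

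**The composite is conditional.** If the correlations fall short of .50, the measures would presumably be analysed separately and the Mullen result would be visible. The concern applies when the composite is formed.

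**Conclusion.** The concern holds in this form: one third of the composite, and probably two thirds, comes from parents who know whether they were treated, and the SAP has no companion analysis that would show whether the directly tested measure agrees. For assumed shifts of 0.2 to 0.4 SD, rejection with no true effect runs from 11% to 38% if both measures are affected and from 6% to 12% if only the MacArthur-Bates is. These ranges rest on alpha .05, r = .65, 30 per arm, ρ of .5 to .7, an equal shift in both active arms and an unbiased Mullen.

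The documents do not support the stronger conclusions that bias will occur, that a positive Aim 2 result would be uninterpretable, or that parent report should be dropped.

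**What to change.** 1. State who completes the Vineland, and whether follow-up Mullen examiners know the arm.
2. Keep the composite. Prespecify the same pretest-adjusted three-group ANCOVA on the Mullen language score alone, reported with its confidence interval beside the composite and the parent-report part.
3. State that, if the Mullen estimate does not support the direction of the composite's active-versus-control effect, the result will be described as resting on parent-reported language. Do not require effects of similar size: at r = .65 and 30 per arm the SE of a pairwise adjusted difference is √.5775 × √(2/30) = 0.20 SD, too wide to judge similarity. Agreement in direction is itself a low bar, which is why the interval should be shown.
4. Rerun the Aim 4 self-efficacy model with the Mullen score as outcome, as a sensitivity analysis.

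The cost is SAP wording and a few extra models on data already planned, with no new visits or measures. The Mullen alone may be less precise than the composite, and the claim about child language may be narrower.

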Protocol for Comparative Efficacy of Self-directed & Therapist-assisted Telehealth Parent
Training Intervention for Children With ASD

NCT02721381

Based on last approval by MSU IRB on 4/6/2020

Risk to Human Subjects

a. Human Subjects Involvement, Characteristics, and Design

A total sample of 90 children with ASD between the ages 18-96 months and their primary caregivers will be recruited for this study. This sample size was determined to be adequate for maintaining adequate power for the proposed statistical analyses, while allowing for some attrition.

Inclusion Criteria for Families: To be eligible for participation, 1) the child must receive a DSM-V-informed clinical diagnosis of Autism Spectrum Disorder, based on the *Autism Diagnostic Observation Schedule* (ADOS). The diagnosis may be provisional for children under age 3 (typically listed as "at risk for ASD"). Children with this classification will be included as well. (2) The child must fall between the ages of 18 - 96 months at enrollment into the study, which will allow for data collection during the period of early intervention and early childhood special education programming. (3) The parent must understand spoken English as the training materials are presented in English.

Exclusion Criteria for Families: (1) Children with ASD who have a history of significant brain injury or known neurological condition in addition to a diagnosis of ASD, significant sensory impairment or major medical problems. These children and their families may require very specific adaptations to the treatment and thus the results will not be representative of children with ASD. This will be determined through review of medical records, diagnostic reports and parent interview. Criteria and data sources for identifying participants are outlined below.

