Power Analysis. A series of power analyses were conducted using Borm, Fransen, & Lemmens⁸⁹ method for estimating sample size for analyses including a covariate. This approach takes into account the degree of association between the covariate and the outcome (r) by adjusting the required sample size required for an analysis without a covariate by $1 - r^2$ and then adding one extra participant per group. In our case, the covariate is the outcome variable as assessed at the pre-test. Analyses predicting parent fidelity (i.e., Aims 1 & 2) assumed a T1 to T2 correlation in fidelity of $r = .35$, and for self-efficacy, the T1 to T2 correlation was assumed to be $r = .75$. Across the aims involving parent fidelity we found that a sample size of 90 participants would provide 80% power to detect moderate to large effects of treatment condition (e.g., Cohen's $f = .32$). For parent self-efficacy a sample of 90 would provide 90%

power to detect moderately sized treatment effects (e.g., $f = .25$). For the child language variables we assumed a correlation between pretest and follow-up of approximately $r = .65$ for each of the three measures. Analyses predicting child language variables at follow-up controlling for pretest language scores (i.e., Aims 2 & 4) indicated that a sample size of 90 participants will have approximately 90% power to detect a moderate effect size ($f = .25$) for treatment condition.

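### Aims 1 and 2 ask how self-directed and therapist-assisted training compare, but no contrast between those two arms is specified, and power is given only for the overall three-group effect

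*Combined protocol and SAP*

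**What the plan says.** In the Statistical Analysis Plan, Aims 1 and 2 open with the same purpose: "To examine the comparative efficacy of self-directed and therapist-assisted" ImPACT Online, on parent outcomes (Aim 1) and child outcomes (Aim 2).

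- **Aim 1** uses a multilevel model with visit as a categorical factor, in which "between-group differences in change in outcomes will be estimated with the group by time interaction".
- **Aim 2**: "ANCOVA will be used to test for mean differences between the three conditions at follow-up", with pretest values as covariates.
- **Aim 3** prescribes simple slopes after a significant moderation interaction. Aims 1 and 2 have no equivalent follow-up step.
- **Aim 5**, which is exploratory, contains the only explicit self-directed versus therapist-assisted term, and its outcome is adherence.

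The Power Analysis section works throughout in Cohen's f for treatment condition. For fidelity, 90 participants "would provide 80% power to detect moderate to large effects of treatment condition" (f = .32). It claims 90% for self-efficacy and about 90% for child language, both at f = .25. It gives no pairwise difference, pattern of means, alpha or dropout rate.

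**The concern.** With three arms, a significant overall test says that some arm differs from some other. It can be driven entirely by both active arms beating control, which says nothing about whether therapist assistance adds anything. Since the contrasts, visits and error control are left open, they could be settled after the data are seen. A reader could also carry the stated 80–90% power over to the head-to-head comparison in the title and aims, which those figures do not describe.

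**Working it through.** **Inputs from the documents**
- Total N of 90 (Human Subjects section): "A total sample of 90 children with ASD between the ages 18-96 months and their primary caregivers will be recruited for this study".
- Three arms (Assignment to Study Group): "participants will be randomly assigned to the one of the three groups using random permuted blocks of 6".
- Power method: "A series of power analyses were conducted using Borm, Fransen, & Lemmens"; the unadjusted sample size is multiplied by 1 − r², "then adding one extra participant per group".
- Fidelity: r = .35, f = .32. Self-efficacy: r = .75, f = .25. Language: r = .65, f = .25.

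**Assumptions, because the documents are silent**
- 1:1:1 allocation, so 30 per arm (blocks of 6 fit this).
- Alpha .05 two-sided.
- No dropout.

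**Step 1. Reproduce the stated power (three groups, 2 numerator df)**

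Stated method: effective N = (90 − 3)/(1 − r²), noncentrality = effective N × f². Direct ANCOVA: noncentrality = 90 f²/(1 − r²), error df = 90 − 3 − 1 = 86.

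| Outcome | 1 − r² | Effective N | Power, stated method | Power, direct ANCOVA | Plan says |
|---|---|---|---|---|---|
| Fidelity | .8775 | 99.1 | 80.9% | 82.1% | 80% |
| Self-efficacy | .4375 | 198.9 | 89.0% | 89.4% | 90% |
| Language | .5775 | 150.6 | 78.1% | 79.0% | about 90% |

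The first two agree with the plan, which supports reading all three as omnibus power. The language figure does not agree. By the stated method, 90% at r = .65 needs about 123 participants (207 × .5775 + 3 = 122.5). Using alpha .10 instead gives 87.1%.

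**Step 2. An omnibus result without a head-to-head difference**

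Let control, self-directed and therapist-assisted means be 0, d, d. The SD of these means is d√2/3, so d = 3f/√2 = 3 × .25/1.414 = .53 SD. Omnibus power depends only on f, so for language it stays at about 79%, while the difference between the active arms is zero.

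**Step 3. Detectable head-to-head difference**

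This needs no pattern of means. With 30 per arm and 86 error df, 80% power requires a standardised difference of .732 (noncentral t, noncentrality d√15).

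- With ANCOVA adjustment, multiply by √(1 − r²). Fidelity: .732 × .937 = .69 SD. Self-efficacy: .732 × .661 = .48 SD. Language: .732 × .760 = .56 SD.
- Aim 1, however, names a model in which pre-treatment is one of the visits. With complete data and equal variances, its group-by-time contrast at post-treatment is a difference in change scores, with variance factor 2(1 − r). Fidelity: .732 × √1.30 = .83 SD. Self-efficacy: .732 × √.50 = .52 SD.

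**Step 4. Head-to-head power at the plan's own f**

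This does depend on where self-directed lies between control and therapist-assisted. Equal spacing gives an adjacent difference of f√1.5 (.392 SD at f = .32, .306 SD at f = .25). Self-directed equal to control gives 3f/√2 (.679 and .530 SD). ANCOVA-adjusted:

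| Position of self-directed | Fidelity | Self-efficacy | Language |
|---|---|---|---|
| Equal to control | 79% | 87% | 76% |
| One quarter of the way to therapist-assisted | 64% | 72% | 60% |
| Midway (equal spacing) | 36% | 43% | 34% |
| Three quarters of the way | 12% | 13% | 11% |
| Equal to therapist-assisted | alpha level | alpha level | alpha level |

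With the change-score variance, the midway row falls to about 26% for fidelity and 38% for self-efficacy.

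**The case against.** The best reply is that this is under-specification and not a wrong test. Much of that stands.

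- **Aim 1.** A reader might infer that the named tests cannot answer the comparative question. That goes too far. A multilevel model with categorical visits yields arm-by-visit coefficients, and under suitable coding one of them is the head-to-head difference in change. The SAP does not call the interaction an omnibus test. What is missing is the choice of contrast.
- **Aim 2.** The wording is most naturally a three-group F test. Pairwise follow-up is unstated, not excluded.
- **Power.** A reader might also infer that the plan conceals head-to-head power of about 34–43%. That range holds only with self-directed exactly midway, and the documents state no pattern of means. They mention primary hypotheses for Aim 1 but do not list them, so the expected pattern cannot be recovered. At the same f, power can be as high as 76–87% if self-directed equals control, and higher still if control lay between the active arms.
- **Error rule.** Testing the overall effect before the pairs is one valid choice among several, and some would not put the central contrast behind a gate.

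None of this supplies the missing contrast. The SAP spells out follow-up testing for Aim 3, so its absence in Aims 1 and 2 leaves the title question without a defined test.

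**Conclusion.** The point holds as a gap in specification. No self-directed versus therapist-assisted contrast is defined for the parent or child outcomes of Aims 1 and 2. The Aim 2 test can be significant (about 79% power for language) with no difference between the delivery forms, and the power statement covers only the overall effect.

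The firmest sizes are the detectable differences, which need no assumed pattern of means: .69, .48 and .56 SD with ANCOVA adjustment, or .83 and .52 SD for the parent outcomes on change from baseline. They rest on 30 per arm, two-sided .05 and the plan's correlations. The protocol expects some attrition, which would make them larger. The documents do not support any single head-to-head power figure; at the plan's f it runs from the alpha level to 76–87% with self-directed anywhere from therapist-assisted to control.

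Separately, the 90% for language is not supported by the plan's own N, r and f at alpha .05. This should be corrected along with the contrasts.

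**What to change.** 1. In Aims 1 and 2, name three planned contrasts: therapist-assisted versus self-directed, and each versus control. Estimate them at post-treatment and follow-up for parent outcomes, and at follow-up for child language, each with a 95% CI. For Aim 1, state the coding and reference arm, and whether the contrast is of change from baseline or baseline-adjusted.
2. State one error rule. A 2-df group test at .05, followed by pairwise tests at .05, controls family-wise error with exactly three groups. That control is per outcome and visit only.
3. In the Power Analysis section, state alpha, say that the figures are omnibus power, and restate language as about 78–79% (N = 90, r = .65, f = .25, alpha .05).
4. Add the head-to-head difference detectable with 80% power, using the variance of the model actually named. If head-to-head power is also quoted, tie it to a stated pattern of means and give the range.

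The cost is a few lines of SAP text with no change to the design. The downside is that the limited head-to-head precision becomes visible.
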